
Overview

The proposed study is a randomized, parallel group clinical trial comparing three months of therapy with continuous positive airway pressure (CPAP) or nocturnal supplemental oxygen (NSO) to optimized medical therapy for treatment of sleep apnea in patients with chronic heart failure. This study will be conducted over 4 years and participants will be recruited from among patients seen at the VA Boston and VA Connecticut Healthcare Systems for a diagnosis of heart failure. A total of approximately 500 patients will be recruited to undergo portable sleep monitoring in order to randomize 39 patients to each active treatment group (CPAP or NSO) and 20 subjects to optimized medical therapy alone. Participation of an individual subject will be approximately 1 week for subjects not meeting criteria for randomization, and 3.5 months for subjects randomized. Participants will be age 18 and over, of either gender, and will have chronic heart failure with left ventricular ejection fraction $\leq 45\%$. No children or other special classes of individuals will be enrolled. All enrolled subjects will be veterans.

Study procedures will include:

- Screening Questionnaires
- Portable Sleep Monitoring
- Baseline (Randomization) Visit, including:
 - Resting Blood Pressure and Pulse
 - Blood draw
 - Anthropometry
 - Heart Failure and Quality of Life Health Questionnaires

- 24 Hour Blood Pressure
- Echocardiogram
- Cardiopulmonary Testing
- Randomization to treatment with one of the following three treatments:
 - Healthy Lifestyle and Sleep Education alone (HLSE)
 - HLSE plus PAP (HLSE-P)
 - HLSE plus nighttime supplemental oxygen (HLSE-O)
- Titration Visit for patients randomized to HLSE-P
- Interim Telephone Contacts
- Final Study Visit with repeat of Baseline Visit procedures

Inclusion criteria for sleep apnea screening:

- Age ≥ 18 years
- Physician diagnosis of chronic HF, American Heart Association Stage C-D
- LVEF $\leq 45\%$
- No change in active cardiac medications for 4 weeks prior to randomization
- Ability to provide informed consent

For continuing to randomization, the following additional inclusion criterion applies:

- Moderate to severe sleep apnea with a prominent central component, defined as an apnea-hypopnea index ≥ 15 events per hour, with a central apnea-hypopnea index > 5 events per hour
- LVEF $\leq 45\%$ indicated at baseline echo test.

Exclusion criteria:

- Hospitalization for acute decompensated HF within previous 30 days

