Ambulatory Blood Pressure Monitoring. Participants will be instructed in the use of an Ambulatory Blood Pressure monitor. The device consists of a blood pressure cuff that is connected by rubber tubing to a small pressure monitoring device that weighs only 9 oz and fits easily in a shirt pocket. The device will be programmed to measure BP at 20 minute intervals during the day and 30 minute intervals at night (11 PM to 7 AM) for the subsequent 24 hours. A pre-paid addressed box will be provided for mail return of the device.

Randomization. After completing testing at the baseline visit, and being instructed in the use of the ambulatory blood pressure monitor, participants will be randomly assigned in a 1:2:2 ratio to one of three treatment groups: **Healthy Lifestyle and Sleep Education** alone (HLSE); HLSE plus Continuous Positive Airway Pressure (CPAP); or HLSE plus nocturnal supplemental oxygen (NSO). Randomization will be performed using permuted blocks, stratified by recruitment site. A SAS program will be used to generate two separate lists of randomization assignments for the two strata. These lists will be

placed into a single data table in a Microsoft SQL Server 2008 database to serve as a lookup table. When a new participant record is created in the database, a trigger is fired on the SQL Server randomization data table that looks up the corresponding stratum using predominant sleep apnea type, picks the next assignment from that stratum, updates the lookup table with the Study ID randomized and the date/time of randomization. Due to the nature of the treatments, blinding of subjects to treatment arm is not possible. The ultrasonographers and physicians overseeing and scoring the echocardiograms and cardiopulmonary exercise tests will be blind to treatment assignment.

Treatment

Healthy Lifestyle and Sleep Education (HLSE Group)

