This study is a randomized clinical trial with three parallel treatment groups, designed to compare the active treatment groups (CPAP and NSO) to the optimal medical management comparator (HLSE). Baseline data will be summarized using standard descriptive statistics for demographic and baseline clinical characteristics by treatment group. Based on our experience with the HeartBEAT Study, the rate of dropouts during the course of the three-month trial is expected to be low and we do not expect dropouts

to be differential with respect to treatment group assignment. The main analysis will include all subjects completing the follow-up examination. For the purposes of a sensitivity analysis, a result of “no change” will be imputed for all drop-outs, and compared to the main analysis.

The analysis for each of the primary outcome measures (LVEF and peak VO₂) will consist of a one-factor analysis of variance comparing the mean changes from baseline in LVEF (or VO₂). As we postulate similar benefits from CPAP and NSO, we will specify two contrasts: CPAP vs. HLSE and NSO vs. HLSE as our primary analyses. In a secondary analysis, we will also compare the effects of CPAP to NSO for the purpose of hypothesis generation for subsequent larger studies. This analysis is a simple analysis of variance, with data transformation or adoption of rank-based inference if approximate normality is not present. While the randomization should achieve approximate balance on potentially confounding conditions, analysis of covariance models that employ adjustments for recruitment site, age, sex, sleep apnea severity, comorbid illness, smoking and alcohol use will be fit to potentially improve the efficiency of the treatment effect estimates. Should a significant difference between treatment and comparator be identified, further exploratory analyses will assess the relation of adherence to therapy to change in outcome measures.

In order to compare the effectiveness of the assigned interventions in controlling sleep apnea over the course of the study, an additional exploratory analysis will compare the change in AHI, change in time in periodic breathing, and change in time at SpO₂ <90% between the baseline and final portable sleep monitoring studies. This analysis will utilize a one-factor analysis of variance. Further exploratory analyses will assess the relation of effectiveness of control of sleep apnea to changes in the primary outcome measures.

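### The randomization paragraph names recruitment site as the stratification factor, but its database lookup picks the stratum by an undefined sleep apnea type; the key actually used must be established

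*Combined protocol and SAP*

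**What the plan says.** The Randomization paragraph, under the baseline visit in the protocol's Work Proposed section, gives the design in one sentence: "Randomization will be performed using permuted blocks, stratified by recruitment site". The next sentence is consistent with that: "A SAS program will be used to generate two separate lists of randomization assignments for the two strata". The paragraph then explains how an assignment is drawn. The lists sit in a lookup table, and when a participant record is created a trigger "looks up the corresponding stratum using predominant sleep apnea type, picks the next assignment from that stratum".

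Three other places bear on which factor is meant:

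- The Overview names two recruiting systems: "participants will be recruited from among patients seen at the VA Boston and VA Connecticut Healthcare Systems".
- The additional criterion for randomization is "Moderate to severe sleep apnea with a prominent central component", set as an apnea-hypopnea index of at least 15 per hour with a central index above 5 per hour.
- The Statistical analysis section makes the primary analysis a "one-factor analysis of variance comparing the mean changes from baseline in LVEF" (and likewise peak VO₂). Supporting covariance models then use "adjustments for recruitment site, age, sex, sleep apnea severity, comorbid illness, smoking and alcohol use".

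**The concern.** Recruitment site and apnea type are different variables, and the same paragraph gives each of them as the sole key to the two lists. A programmer, auditor or author following the text has to choose one.

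The second factor cannot be applied from the documents. No cut-off says when one type of apnea predominates. The nearest wordings elsewhere are the eligibility threshold above and a description of the population of an outside trial of adaptive servo-ventilation; neither defines strata.

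Three things are at stake:

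- whether the stratification factor that is eventually reported is the one that was used;
- whether balance by site was assured in a control arm of 20 that serves both primary contrasts;
- which stratification term belongs in the primary model, since the planned one-factor analysis contains none.

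**Working it through.** **1. The plan's count of two lists.** The number of strata is the product of the factor levels. Site alone gives 2 and matches. Type alone, if it has two levels (an assumption), also gives 2 and matches. Both factors crossed give 2 × 2 = 4 and do not match. The count rules out crossing but does not separate site from type.

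**2. The other evidence.** For site: it is the factor stated outright, and it is a covariate in the adjusted models, where apnea severity appears but apnea type does not. Neutral: the eligibility threshold admits patients with mostly obstructive events and patients with mostly central events, so a split by type is possible in this population.

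**3. Site balance if type was the key.** From the plan: 39 + 39 + 20 = 98 randomized, 20 to HLSE (the control arm). Assumed: 49 patients per site, block size 5 or 10, type unrelated to site.

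- Type key: the HLSE count at one site is approximately hypergeometric, with SD = √(20 × 0.25 × 78/97) = 2.01 and a 95% range of 6 to 14.
- Site key, blocks of 5: 49 patients fill 9 blocks plus 4 of the next 5 places. The count is 9 plus a Bernoulli(0.8) variable, so 9 or 10, with SD √(0.8 × 0.2) = 0.40. Blocks of 10 also give 0.40.
- In simulation (4,000 runs per setting, blocks of 5), the type-key SD stays at about 1.7 to 2.0 for site splits of 50:50 to 70:30, type splits of 50:50 to 80:20, and type prevalence differing between sites by 0 to 40 points.

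**4. Cost of that imbalance.** In 12,000 simulated trials (three-arm model, 98 patients), a type key makes the site-adjusted SE of the HLSE-CPAP contrast 0.5% larger than the unadjusted SE on average, and 2% larger at the 95th percentile. With a site key the average ratio is 1.0001.

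**5. Leaving site out of the primary model when the lists were blocked by site.** The Sample size and power section gives 34 and 17 evaluable, SD 4.8, a 5-point LVEF difference and a 2.5% level. The planned SE is 4.8 × √(1/34 + 1/17) = 1.426. The plan's 90% power is 89.7% by the normal approximation. With the three-arm error term (34 + 34 + 17 − 3 = 82 df) the noncentral t gives 88.71%. With a site term (81 df) and no site difference it is 88.70%, a cost of about 0.01 point.

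Let d be an assumed site difference in LVEF change, with equal sites. The variance between sites is d²/4. Site blocking removes it from the true error of the contrast, but a model without site still counts it in the estimated SE. Let r be the ratio of the SD with site variance to the SD without it. Then actual size = 2 × P(T₈₂ > t₀.₉₈₇₅ × r).

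The plan does not say whether 4.8 includes variation between sites, so both readings are shown:

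| Reading of 4.8 | d | r | Actual size | Power, site omitted | Power, site term |
|---|---|---|---|---|---|
| Within-site SD, r = √(4.8² + d²/4)/4.8 | 1 | 1.005 | 2.42% | 88.5% | 88.7% |
| | 2 | 1.021 | 2.21% | 87.7% | 88.7% |
| | 3 | 1.048 | 1.90% | 86.5% | 88.7% |
| Whole within-arm SD, r = 4.8/√(4.8² − d²/4) | 1 | 1.005 | 2.42% | 88.8% | 89.1% |
| | 2 | 1.022 | 2.20% | 89.2% | 90.1% |
| | 3 | 1.053 | 1.85% | 89.9% | 91.8% |

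The gain from the site term is 0.2 to 2.2 points on the first reading and 0.2 to 2.0 on the second.

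**The case against.** The strongest reply is that this is one stray clause in a paragraph that names its factor plainly, and that little depends on it. Sample size, alpha and allocation ratio are unchanged, the supporting covariance models already adjust for site, and even a wrongly keyed trigger costs about 0.5% in SE on average. All of that stands and limits the weight of the point. It does not make the paragraph usable: this is the allocation rule, and nothing elsewhere resolves it.

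A second reply is that leaving the stratification factor out of the primary model would deserve comment even if the paragraph were consistent. That is true, and it adds nothing to the seriousness of the contradiction. It belongs here only because the right term cannot be named until the key is known.

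A third concerns power. A reader might infer that omitting site pulls power below the planned figure. That happens only if 4.8 is the SD within sites. The Sample size and power section assumes it for each group, which reads more naturally as the whole within-arm SD. On that reading power with site omitted is 88.8% to 89.9%, so nothing is lost against the plan; the site term is simply a gain.

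A reader might also infer that the clause is certainly a slip and that site was used. The documents do not support that certainty. A two-level type fits two lists and the eligible population, and the Background describes different effects of oxygen in obstructive and central apnea, which makes type a plausible stratifier.

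**Conclusion.** The contradiction is real and the allocation rule is wrong as written. Site is the likelier intent, on the strength of the explicit sentence and the covariate list, but this is an inference. The opposite inference, that the stated site stratification was not delivered, is equally unsupported: it would follow only if the trigger was built as the clause reads, and the documents do not show what was programmed.

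The inferential impact is low. Under either key there is no bias in expectation. If type was the key, what is lost is assured site balance (6 to 14 control patients at one site instead of 9 to 10, with equal sites and type unrelated to site). If site was the key and stays out of the primary model, the nominal 2.5% test runs at about 2.4% to 1.9% for an assumed site difference of 1 to 3 points, which is slightly conservative. The documents give no site difference, site split or block size; those values are assumptions. The point is worth fixing because the reported stratification factor may be wrong and the remedy is cheap.

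**What to change.** The order matters, because the check decides the wording.

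1. Inspect the trigger code and the assignment log, and record which key has been used to date.
2. If it was site, change the lookup clause to recruitment site.
3. If it was apnea type, define what makes a type predominant, correct the stated stratification factor, and report that balance by site was not assured.
4. In either case, put the factor actually used into the primary LVEF and peak VO₂ models, and not only into the supporting covariance models.

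The cost is one check of code and log, a corrected sentence (plus a definition if type was used), and 1 df. No extra patients are needed. A small database change arises only if the key proves wrong, and in that case the factor reported for patients already randomized may also need correcting.

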The proposed study is a randomized, parallel group study comparing three months of therapy with optimized medical therapy plus continuous positive airway pressure (CPAP) or nocturnal supplemental oxygen (NSO), respectively, to optimized medical therapy alone for patients with comorbid sleep apnea and chronic HF with reduced ejection fraction. The primary study outcomes are: (1) left ventricular ejection fraction (LVEF) measured by echocardiography, which is identified by the American College of Cardiology and American Heart Association as the single most useful test in the evaluation of patients with HF (26) and which has been shown in several studies to increase significantly over 4 to 12 weeks of therapy with CPAP or NSO in patients with heart failure and central sleep apnea (41), and (2) peak oxygen consumption on cardiopulmonary exercise testing (peak VO₂), a valid and reproducible measure of functional capacity that has also been reported to increase following ASV or NSO (47, 50, 58, 59). The primary analysis will compare each of the active treatment arms to the optimized care control group.

Sample selection

The target population is veterans with American Heart Association Stage C or D chronic HF with reduced ejection fraction and comorbid sleep apnea. Patients will be recruited from among those patients enrolled in the VA Boston or VA Connecticut Healthcare Systems who carry a diagnosis of chronic HF. Potential participants will be identified via the computerized patient record system, by searching on the diagnosis of HF using diagnostic codes 428.0-428.9. Medical records will be screened to confirm the diagnosis of HF and document reduced LVEF by echocardiogram, nuclear gated blood pool scan, or ventriculogram.

Recruitment

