Echocardiogram. Standard transthoracic 2-dimensional and Doppler echocardiography will be performed using a Philips IE33 cardiac ultrasound (Philips Healthcare, Andover, MA) to estimate cardiac dimensions, mass, and systolic and diastolic function. All images will be captured in 3-beat loops for patients in sinus rhythm, 5-beat loops for those in atrial fibrillation. M-mode measurements of LV dimensions will be performed and analyzed according to the American Society of Echocardiography recommendations (61). LVEF will be measured using the modified Simpson's method. The interventricular septum thickness (IVST), posterior LV wall thickness (LVPWT), and left ventricular internal diastolic diameter (LVIDD) will be measured at end-diastole, and left ventricular mass calculated as $0.8*(1.04*[(\text{LVIDD}+\text{IVST}+\text{LVPWT})^3-(\text{LVIDD})^3]+0.6)$. We will determine standard measures of diastolic function including E and A wave velocities, deceleration time, and pulmonary venous flow velocities, as well as utilize tissue Doppler imaging to detect abnormalities of diastolic function. Pulmonary artery systolic pressure will also be estimated utilizing Doppler measurements. For individuals with unclear images, or who have required contrast in the past, contrast will be used.

Cardiopulmonary Exercise Testing. Treadmill exercise testing in association with air-gas-exchange, generally considered to be an optimal gauge of functional capacity, will be supervised by [name] (co-investigator), who has used this technique extensively in both clinical and clinical-research applications. All patients will be assessed by a cardiologist for clinical stability immediately before the exercise stimulus. An intravenous catheter will be placed in advance of the procedure per routine as a routine safety precaution. A motor-driven treadmill will be used and exercise will follow a modified Balke protocol. A bicycle ergometer will be used for those participants who are unable to walk on a treadmill but are capable of bicycle exercise (e.g., due to balance problems). A lightweight disposable pneumotach

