device will be positioned in the participant's mouth during the exercise VO₂ peak, VO₂ at anaerobic threshold and VE/VCO₂ will be measured using a metabolic cart. During exercise, electrocardiogram waveforms and hemodynamics (maximum heart rate and blood pressure) will be monitored. Patients will exercise to their symptomatic limits, with encouragement to achieve a respiratory exchange ratio >1.0 (consistent with high physiological workload). However, if there are any signs of medical instability, the cardiologist will end the test before the symptomatic endpoint is achieved. In any instances of submaximal workload, analysis would focus on VO₂ at anaerobic threshold, VE/VCO₂ and other indices that do not depend on peak exercise performance.

Questionnaires

- Medical Outcomes Study SF36 Health-related Quality of Life Questionnaire. Each subject will complete the SF36 at their baseline and 3 month follow-up appointment. This questionnaire is a multi-purpose, short-form health survey that is widely used in research to estimate specific disease burden and to compare disease-specific benchmarks with general population norms. The questionnaire consists of 36 questions and provides an 8-scale profile of functional health and well-being scores (62).
- Kansas City Cardiomyopathy Questionnaire. Each subject will complete this questionnaire at their baseline and 3 month follow-up appointment. This questionnaire is widely used to evaluate quality of life in heart failure patients. It consists of 23 items which assess the level of impact of physical symptoms in this population such as shortness of breath, fatigue, peripheral edema, and difficulty sleeping. It also assesses the impact of psychological symptoms like anxiety and depression, as well as social functioning (63).
- CHAMPS Physical activity questionnaire for older adults (64). Each subject will complete this questionnaire at their baseline and 3 month follow-up appointment. This questionnaire is used to assess physical activity in our population.
- Health Questionnaire. Each subject will complete this questionnaire at their baseline and 3 month follow-up appointment. This questionnaire is used to collect data about medical history, and general but important health indicators, e.g., alcohol use, sleep quality, and restless leg symptoms.

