identifiers. Only study personnel will have access to research data, which is kept either in locked cabinets, in password-protected computers in locked offices, or on secure password-protected drives located behind the VA firewall or at the Center for Clinical Investigation at Brigham & Women's Hospital. All personal data will be stored separately from de-identified research data, and will be stored in password-protected files behind the VA firewall or in locked cabinets within the VA. Blood and specimens will be stored using de-identified bar codes at the VA Boston and shipped to [name] laboratory, the VA Boston clinical lab for testing. Once the assays have been run on the samples, any leftovers will be destroyed.

Risks from cardiopulmonary exercise testing will be minimized by close physician supervision of testing, which will be performed by trained technicians in the Cardiopulmonary Exercise Laboratories at the VA Boston and VA Connecticut HCS sites, with emergency equipment readily available. Although patients will be encouraged to exercise to their symptomatic limits, if there are any signs of medical instability, the cardiologist will end the test before the symptomatic endpoint is achieved.

Phlebotomy will be performed by trained phlebotomists.

All CPAP devices will be equipped with heated humidifiers to minimize drying, and attention will be paid at set-up to identifying a best-fit mask to minimize mask discomfort and air leaks. Subjects will be contacted at weeks 1, 2, 4 and 8 to identify any early problems with treatment and to ascertain any adverse events, in particular the onset of dangerous levels of sleepiness. Participants will be extensively counseled at the baseline visit on safety measures related to excessive sleepiness. Participants randomized to NSO will be counseled on risks of fire from use of oxygen near open flames, including cigarettes.

Potential Benefits of the proposed Research to Human Subjects and Others

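### The protocol does not say that the technicians who perform the exercise tests are blind, although peak VO2 is an effort-dependent primary outcome and participants know their arm

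*Combined protocol and SAP*

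**What the plan says.** **Who is blind.** The Randomization paragraph accepts that "Due to the nature of the treatments, blinding of subjects to treatment arm is not possible". It then lists the blinded staff: "The ultrasonographers and physicians overseeing and scoring the echocardiograms and cardiopulmonary exercise tests will be blind to treatment assignment". The list contains ultrasonographers and physicians, and no other section adds to it.

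**Who runs the exercise tests.** Protection against risks says that "Risks from cardiopulmonary exercise testing will be minimized by close physician supervision of testing", and of the testing itself, "which will be performed by trained technicians in the Cardiopulmonary Exercise Laboratories". It does not say whether those technicians are blind.

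**What is measured.** Study Design makes "peak oxygen consumption on cardiopulmonary exercise testing" the second primary outcome, beside LVEF. The Cardiopulmonary Exercise Testing section says: "Patients will exercise to their symptomatic limits, with encouragement to achieve a respiratory exchange ratio >1.0". It does not say who encourages, or in what words. The same section provides that "All patients will be assessed by a cardiologist for clinical stability immediately before the exercise stimulus". Where the workload is submaximal, the analysis moves to VO2 at anaerobic threshold, VE/VCO2 and "other indices that do not depend on peak exercise performance".

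**When.** Baseline testing is complete before allocation. The procedures are repeated after 12 weeks (Final study visit).

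**The concern.** For echocardiography, the list covers both the person who acquires the images and the person who scores them. For exercise testing, it covers the physicians who oversee and score, but not the technicians who perform the test. This asymmetry falls on the primary outcome more open to influence during measurement, because peak VO2 depends on how hard the patient is willing to work.

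Participants know their arm and meet the exercise staff face to face at the final visit. Nothing asks them to keep their treatment to themselves. A technician could learn the arm from a remark, and so could the cardiologist who assesses the patient just before the test.

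If patients known to be on CPAP or oxygen were pushed harder than those on education alone, their 12-week peak VO2 would rise with no change in capacity. Baseline is measured before allocation, so the whole difference would enter the change from baseline, which is what the primary analysis compares. If both active arms were encouraged more, both primary contrasts would move in favour of treatment.

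**Working it through.** **Step 1. Set the sections side by side.**

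| Task | Echocardiogram | Exercise test |
|---|---|---|
| Performs the test | Ultrasonographer: blind | Technician: not stated |
| Oversees | Physician: blind | Physician: blind |
| Scores | Physician: blind | Physician: blind |
| Encourages the patient | Not applicable | Person not named, no script |
| Patient | Knows the arm | Knows the arm |

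The gap is one cell for performing the test and one for encouraging.

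**Step 2. See what the existing safeguards cover.**
- Blinded scoring protects the reading of the test. It cannot correct effort already given.
- The fallback to effort-independent indices applies only to submaximal tests. Effort can still differ among tests that pass an RER of 1.0.
- The covariates listed under Statistical analysis are site, age, sex, sleep apnea severity, comorbid illness, smoking and alcohol. None measures effort.

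**Step 3. Reproduce the plan's peak VO2 power.** Inputs from Sample size and power: 34 evaluable per active arm, 17 in HLSE, two-sided 2.5%, difference 0.92 SD, stated power 80%.
- Standard error in SD units: √(1/34 + 1/17) = 0.297.
- Noncentrality: 0.92 / 0.297 = 3.097.
- Normal approximation: critical value 2.241, power 80.4%.
- Noncentral t with 34 + 17 − 2 = 49 df: critical value 2.312, power 78.1%.

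Both lie within 2 points of the stated figure. With the plan's SD of change of 2.5 ml/kg/min, 0.92 SD is 0.92 × 2.5 = 2.3 ml/kg/min.

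**Step 4. Illustrate a bias.** The documents give no size for differential encouragement, so the shift *b* below is an assumption. The true effect is set to zero. The noncentrality is (b / 2.5) / 0.297, and the rejection probability is that of the plan's two-sample t-test with 49 df at two-sided 2.5%.

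| Assumed shift, ml/kg/min | In SD units | Noncentrality | Rejection per contrast |
|---|---|---|---|
| 0 | 0 | 0 | 2.5% |
| 0.25 | 0.1 | 0.337 | 3.3% |
| 0.5 | 0.2 | 0.673 | 5.8% |
| 0.75 | 0.3 | 1.010 | 10.5% |
| 1.0 | 0.4 | 1.347 | 17.7% |

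A shift of 0.5 is 0.5 / 2.3, about 22% of the difference that the plan is powered to detect.

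**Step 5. Both contrasts together.** A simulation with the same shift in both active arms and one shared HLSE group gives the chance of at least one significant peak VO2 contrast: about 4.4% with no shift, 9.6% at 0.5 and 26% at 1.0 ml/kg/min. Both contrasts shift because both active arms are assumed to receive the extra encouragement. Sharing the control correlates the contrasts but creates no bias by itself.

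**The case against.** A reader might infer that unblinded staff run the exercise tests. The documents do not say so; they are silent. Several details make routine knowledge of the arm less likely. The assignment sits in a database table. CPAP adherence review belongs to the Research Coordinator, and CPAP titration to Sleep Laboratory technicians, whereas exercise tests take place in a separate laboratory. This stands: the supported statement is that the technicians' blinding is not specified.

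A reader might also infer that the technician gives the encouragement. That too is unstated. A blinded physician supervises the testing and may be the one who encourages. This is a real safeguard, but the protocol does not assign encouragement to that physician, and the physician can learn the arm from the participant.

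A third tempting reading is that nothing in the trial could reveal such a bias. That goes too far. VO2 at anaerobic threshold and VE/VCO2 are measured in the same test, and LVEF is acquired and scored blind. A gain in peak VO2 with no movement in these would be a warning. It would not be a correction, because a treatment could also improve peak VO2 alone.

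Finally, the size of the shift is assumed, and at 0.25 ml/kg/min the effect on the error rate is small. Participants' own effort may also differ by arm whoever runs the test, and blinding technicians cannot remove that. Both points stand. They limit what can be claimed and what the fix can achieve, but they are not reasons to leave the blinding of these staff unstated.

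**Conclusion.** The point holds as a gap in specification and a cheap improvement. The staff who perform the test for one primary outcome are missing from the only list of blinded staff, encouragement is unscripted and assigned to nobody, and participants are not asked to withhold their arm. Differential encouragement at the 12-week test is therefore possible under the plan as written. The documents do not show that it occurs.

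The existing safeguards are partial. The rejection rates of 3.3% to 17.7% per contrast illustrate shifts of 0.25 to 1.0 ml/kg/min and do not estimate a bias in this trial. They rest on the plan's SD of 2.5 and 34 versus 17 evaluable, no true effect, and the assumption that staff learn the arm and act on it. The sample size and the planned contrasts are unaffected.

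**What to change.** 1. In the Randomization paragraph, add the exercise-test technicians to the staff who are blind to assignment. If they are blind already, this only records it.
2. Before the final visit, tell participants not to mention their treatment to echocardiography or exercise staff.
3. In the Cardiopulmonary Exercise Testing section, require one fixed encouragement script at baseline and at 12 weeks.
4. State that staff who handle devices or make adherence calls do not encourage during the test.
5. Report peak RER by arm at both visits. The test already aims at an RER target, so this uses data already collected and shows whether effort differed.
6. Acknowledge participants' own expectancy as a remaining limitation of the peak VO2 result.

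The cost is protocol wording, a short participant instruction, a script and one descriptive table. One downside is that a treatment-related problem raised on the test day has to be routed to the coordinator.
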